- The 3rd generation tourniquet system features a built-in LOP measurement capability. This allows a personalized tourniquet pressure for each individual patient and eliminated the need to account for cuff width, limb size or blood pressure.

Determination of Leg dominance (Melick, 2017)

Since mobility is a bilateral mobilizing task, the leg dominance will be defined by the participant's preferred leg to shoot a ball when being asked the following question: "If you would shoot a ball on a target, which leg would you use to shoot the ball?"

Determination of completeness of training

80% of the whole course of in-patient additional muscle strength training (i.e. 10 out of 12 sessions)

Determination of acceptance of program

5-point Likert scale will be given to participants after the additional muscle strength training (i.e. very like, like, no comment, dislike, very dislike)

Data collection timepoint

- Baseline
- After completeness of training (i.e. at least 10 sessions of training)

Clinical investigations

- Laboratory tests at baseline and post training program
 - ✧ Clotting profile, Complete blood count (CBC), liver function test (LFT), renal function test (RFT), serum creatinine kinase level (CK), serum lactic acid level, C-reactive protein (CRP)
 - ✧ Estimated 32ml of venous blood in total will be needed for both pre and post training blood tests.
 - ✧ Myoglobin in urine
- Spirometry before discharge of current admission

Primary outcome:

Localized Muscle Strength (Robles, 2011; Hul ,2004)

- Muscle strength is operationally defined as subject's capability for the exertion of force or torque to an external dynamometer over a specified period of time. (Kroemer, 1980)
- Maximal voluntary isometric contraction (MVIC) of knee extension of the dominant leg, with a unit Newton (N), will be assessed by computer dynamometry.

Secondary outcomes:

- **Functional test**
 - ✧ Short physical performance battery (SPPB) (Mora, 2015)
Gait speed with 4m distance, Balance test & repeated chair stands test
 - ✧ 6-minute walk test (Holland, 2010)
- **Systemic muscle strength** (Jeong, 2017; Yu, 2017)
 - ✧ Hand grip strength, a non-invasive marker of systemic skeletal muscle strength and function, is assessed by handheld grip dynamometer of dominant hand
- **Health related quality of life**
 - ✧ Self-administered Chinese version of COPD assessment test (CAT) (Karlah,2016)
- **Acceptability of BFR-RE**

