 - ✧ Pain by visual analog scale (0-10) before, immediate and 5-min post exercise
 - ✧ Participant's acceptance by a Likert 5-point categorical scale after the whole program
- **Feasibility of BFR-RE**
 - ✧ Examination of drop-out rate and reasons of drop-out in those discontinuing the training
- **Unplanned readmission rate within 1 month of discharge for COPDAE**

Data analysis

SPSS version 17.0 will be used for statistical analysis.

The comparison of baseline characteristics of subjects across the 2 groups will be tested by independent t-test for continuous variables (e.g. age, anthropologic data, maximum voluntary isometric contraction of knee extension of dominant leg, hand grip strength of dominant hand, laboratory test results, spirometry data, 6-minute walk test, COPD Assessment test (CAT), etc.), Chi-square test for nominal variables (e.g. presence of myoglobin in urine, etc.).

For testing between-group and within-group changes after Blood flow restriction resistance exercise (BFR-RE), multivariate repeated measures ANOVA will be used.

All continuous variables are presented as mean \pm SD (standard deviation). The level of statistical significance was set at $p < 0.05$.

Sample size calculation

A priori power analysis (calculated by G*Power 3.1.9.5) showed that in order to have a power of 80% to detect a difference of medium effect (f^2 : 0.22) of muscle strength gain (Cook, 2017) at the 0.05 level of significance, 18 patients is needed in each group. If a dropout rate of 30% is estimated, 48 patients in total will be needed for the study.

Randomization

Participants are randomized into one of the two treatment groups. A computer compiles randomization list. Based on randomization, envelopes are made with participant number, including allocation of patients to BFR-RE vs. without BFR-RE. The envelopes are opened after inclusion for the individual participant only. The randomization list is kept in a sealed envelope.

Stratification of participants into two groups by maximum voluntary isometric contraction (MVIC) at baseline before randomization will be done. The cutoff for the stratification will be determined from the data in the recent service.

Blinding

Participants, doctors, nurses and involved Physiotherapists are for obvious reasons not blinded, but assessments at recruitment and on discharge will be carried out by blinded Physiotherapists without knowledge of treatment group.

Interruption

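### Enrolling 48 patients covers 25% drop-out, not the stated 30%: about 34 completers are expected against the 36 that the plan requires

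*Combined protocol and SAP*

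**What the plan says.** The Sample size calculation section sets the target for 80% power: "at the 0.05 level of significance, 18 patients is needed in each group". The effect is described as a "medium effect (f^2 : 0.22) of muscle strength gain". With two groups the requirement is 36 patients with usable data. The next sentence makes the allowance for losses: "If a dropout rate of 30% is estimated, 48 patients in total will be needed for the study". No inflation formula is given.

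The section Data collection timepoint lists two occasions, baseline and "After completeness of training (i.e. at least 10 sessions of training"). The Blinding section also mentions blinded assessments at discharge. Nothing in the protocol provides for replacing patients who drop out, for imputing missing outcomes, or for any other margin above 36.

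**The concern.** A drop-out rate applies to the patients enrolled. To finish with a given number after losing a fraction d, the required number is divided by 1 − d. Multiplying it by 1 + d gives too few, and the gap widens as d grows. At 30% the two rules differ visibly, and 48 agrees with the multiplication.

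A reader will take 48 to mean that 80% power is protected up to 30% drop-out. As written, it is not. The drop-out rate is also a feasibility outcome of this trial, so the planned rate will be set beside an observed one. The protocol should therefore state correctly what rate its sample size can absorb.

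**Working it through.** **Inputs, all from Sample size calculation**
- Evaluable patients required: 18 per group, 2 × 18 = 36 in total.
- Drop-out rate: 30%, so retention is 0.70.
- Stated total to enrol: 48, or 24 per group. Equal allocation is implied by the equal group sizes.

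**1. Reproducing the plan's figures**
- Base size: reading f² = 0.22 as a two-group comparison, f = √0.22 = 0.469 and d = 2f = 0.938. The normal approximation, two-sided 5% and 80% power, gives n = 2 × (1.960 + 0.842)² / 0.938² = 17.8, rounded up to 18 per group, as stated. (The exact t test gives 19; the protocol does not name the test.) The rest of this check takes 18 as given.
- Total: 18 × (1 + 0.30) = 23.4, rounded up to 24 per group; 2 × 24 = 48. This matches the stated total, but that it was the rule used is an inference.

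**2. What 48 delivers at 30% drop-out**
- Expected completers: 48 × 0.70 = 33.6, or 16.8 per group.
- Shortfall: 36 − 33.6 = 2.4.
- Drop-out that 48 absorbs exactly: 1 − 36/48 = 0.25.

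**3. What 30% drop-out requires**
- 18 / 0.70 = 25.7, rounded up to 26 per group, 52 in total.
- Check: 52 × 0.70 = 36.4, which is at least 36.
- Rounding does not explain the difference: the unrounded total is 36/0.70 = 51.4, still above 48.

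**4. Size of the effect (illustrative)**

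These figures accept the plan's premise that 18 + 18 gives exactly 80% power, and assume a t test comparing gain between the groups. The effect is solved from that premise (noncentral t), then power is recalculated at the smaller sizes.

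| Completers | Two-sided 5% (d = 0.961) | One-sided 5% (d = 0.846) |
|---|---|---|
| 18 + 18 | 80.0% | 80.0% |
| 17 + 17 | 77.6% | 77.9% |
| 17 + 16 | 76.2% | 76.7% |

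The loss is about 2 to 4 percentage points.

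If patients drop out independently with probability 0.30, the exact binomial chance of at least 36 completers is 28% with 48 enrolled and 61% with 52. Requiring at least 18 in each group separately, the chances are 15% with 24 per group and 39% with 26 per group.

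**The case against.** The arithmetic cannot be disputed, so the case on the other side concerns weight.

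- **The gap is small.** It amounts to 2.4 expected completers or 4 recruits, and the 30% is itself an estimate without a source. This stands, and it is why the point is minor.
- **Drop-outs may not be lost to analysis.** The protocol does not define drop-out for the sample size. Under Feasibility the term refers to stopping training, and a patient who stops might still be assessed at discharge. This stands in part: the power loss depends on drop-outs having no post-training measurement. It does not rescue the sentence, because an allowance for drop-out only makes sense if drop-outs are lost to the 36, and the only listed post-baseline timepoint follows at least 10 sessions.
- **The power figures rest on an unstated test and sidedness.** Data analysis plans a repeated measures ANOVA, and no correlation between measurements is given. With f² = 0.22 taken directly (d = 0.938), two-sided power is 78.1% at 18 + 18 and 75.6% at 17 + 17; one-sided it is 86.7% and 84.9%, so 80% would survive. This stands: the power figures only illustrate the scale.
- **The binomial comparison proves little.** Sizing to an expected number never guarantees it, and even 52 misses 36 in 39% of cases. This is fair, and the conclusion does not rely on it.
- **Restating the allowance adds no completers.** This is also true. If 30% is the real expectation, the candid wording is the one that states the expected shortfall.

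**Conclusion.** The concern holds. Three stated numbers, 18 per group, 30% and 48, are mutually inconsistent: 48 enrolled patients absorb 25% drop-out, and at 30% they leave 33 or 34 completers where 36 are required. This conclusion needs no assumption about the test, its sidedness, the effect size or how 18 was derived. It needs only that drop-outs do not count towards the 36, which the sentence itself implies.

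The consequence is minor: a loss of about 2 to 4 points from a nominal 80%, conditional on the two-group model and on drop-outs being unmeasured. There is no shortfall if drop-out turns out to be 25% or less.

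**What to change.** Rewrite the last sentence of Sample size calculation in one of two ways, keeping 48:

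- say that 48 patients in total allow for a drop-out rate of 25%; or
- keep 30% and say that about 34 evaluable patients are then expected, fewer than the 36 needed for 80% power.

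The 25% option suits a sponsor who can justify that rate; the protocol currently offers no basis for it. Keeping 30% is the more candid choice if that is what the sponsor expects. For reference, the total that matches 36 evaluable patients at 30% drop-out is 52, four more than planned.

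Either change costs one sentence, with no extra patients and no change to the recruitment period. The price is an openly lower tolerance for drop-out if 25% is stated, or openly lower expected power if 30% is kept.

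### Randomisation is stratified by baseline MVIC, but the planned between-arm ANOVA includes neither the stratum nor baseline MVIC as a covariate, which gives up some power, mainly on the primary outcome

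*Combined protocol and SAP*

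**What the plan says.** The combined protocol and SAP addresses this in three places.

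- **Randomization.** "Stratification of participants into two groups by maximum voluntary isometric contraction (MVIC) at baseline before randomization will be done". The cutoff is left open: "The cutoff for the stratification will be determined from the data in the recent service". On how the sequence is made, the section says "A computer compiles randomization list". It mentions neither blocks nor a separate list per stratum.
- **Primary outcome and Data collection timepoint.** The stratifying variable is also the primary outcome: "Maximal voluntary isometric contraction (MVIC) of knee extension of the dominant leg, with a unit Newton (N), will be assessed by computer dynamometry". Outcomes are collected at baseline and once more: "After completeness of training (i.e. at least 10 sessions of training").
- **Data analysis.** Apart from baseline t-tests and chi-square tests, the whole between-arm plan is: "For testing between-group and within-group changes after Blood flow restriction resistance exercise (BFR-RE), multivariate repeated measures ANOVA will be used". No stratum term, covariate or adjusted model appears there or elsewhere in the document.

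**The concern.** Stratifying by a factor declares that it is expected to predict outcome. If the analysis leaves it out, the variance it explains stays in the residual. That has two possible consequences.

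- **Power.** The comparison is less precise than the data allow, whether or not the arms are balanced on the factor.
- **Calibration.** If allocation really is balanced within strata, the treatment estimate varies less than the unadjusted model assumes. The reported standard error is then too large and the test rejects less than 5% of the time under the null.

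The trial is small: 18 per group are wanted for 80% power, and 48 patients less 30% drop-out leaves about 34. A few points of power from a variable already measured on everyone are worth having.

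**Working it through.** **1. The plan's own figure.** Sample size calculation gives f² = 0.22 and 80% power, and "at the 0.05 level of significance, 18 patients is needed in each group". Two-sided testing is assumed.

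- f = √0.22 = 0.469, so d = 2f = 0.938 and d² = 0.88.
- n per arm = 2(1.960 + 0.842)²/0.88 = 17.8, which rounds up to 18. The figure is reproduced.
- The exact noncentral calculation gives 19 per arm, and 78.1% power at 36 in total.
- Drop-out: 18 × 1.3 = 23.4, which rounds up to 24 per arm, or 48. Completers expected: 48 × 0.7 = 33.6.

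**2. What the planned test is.** With two time points, group-by-time has one degree of freedom. The multivariate and univariate forms coincide, and both equal a two-sample t-test on change. Adding the stratum and its stratum-by-time term equals regressing change on group and stratum.

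**3. How much the stratum explains for MVIC.** The documents give no correlation, so the pre-post correlation ρ is assumed. Equal pre and post SDs, bivariate normality and a median cutoff are also assumed.

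- Correlation of change with baseline: r = −√((1−ρ)/2).
- Share of change variance explained by a median-split stratum: R² = (2/π)r².
- SE ratio, unadjusted to adjusted: 1/√(1−R²).

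Power below is for 18 per arm, with the effect set so that the planned test has a nominal 80%.

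| ρ | r | R² | SE ratio | Power with stratum | Power with continuous baseline |
|---|---|---|---|---|---|
| 0.5 | −0.50 | 0.159 | 1.09 | 86.3% | 89.8% |
| 0.7 | −0.39 | 0.095 | 1.05 | 83.7% | 85.9% |
| 0.8 | −0.32 | 0.064 | 1.03 | 82.4% | 83.9% |
| 0.9 | −0.22 | 0.032 | 1.02 | 81.2% | 81.9% |

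Hand check at ρ = 0.5: (1.960 + 0.842) × 1.0905 − 1.960 = 1.096, and Φ(1.096) = 86.3%.

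**4. Simulation with balance within strata** (20,000 trials per scenario, about 18 per arm, blocks of 4 assumed, no drop-out).

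| ρ | Unadjusted SE excess | Type I error | Power: planned | With stratum | With continuous baseline |
|---|---|---|---|---|---|
| 0.5 | about 7% (0.331 against 0.309) | 3.4% | 81.7% | 86.3% | 89.5% |
| 0.7 | 4-5% | 4.1% | 80.9% | 83.9% | 85.6% |
| 0.9 | about 1% | 4.8% | 80.5% | 81.2% | 81.5% |

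The gains from the stratum are 4.6, 3.0 and 0.7 points.

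**5. Without balance within strata** (ρ = 0.5). The model SE is 0.331 against a true SD of 0.335, and type I error is 5.0%. The standard error is not too large. Power still rises from 80.0% to 85.3% with the stratum.

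**6. After drop-out** (48 randomised in blocks within strata, 30% lost at random). Loss partly undoes the balance. As a rough check, if 30% of the chance imbalance returns, the SE ratio is about 1/√(1−0.7R²). That is 1.02 at r = 0.3 (R² = 0.057) and 1.06 at r = 0.5 (R² = 0.159). Simulation gives an excess of about 2-5% and type I error of about 4.0-4.5% over that range. A second run gave 0.6% and 4.8% at r = 0.3, and 4.9% and 3.9% at r = 0.5, so these figures are approximate. The power gain is about 1.5 to 5 points at r = 0.3 to 0.5, with or without blocks. At r = 0, adjustment loses about 0.4 point with blocks and 1 point without.

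**7. Secondary outcomes.** Each is analysed as change from its own baseline, so r is the correlation of that change with baseline MVIC. From a nominal 80%, adding the stratum gives 79.9% (r = 0), 80.2% (0.1), 80.9% (0.2), 82.2% (0.3) and 86.3% (0.5).

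**The case against.** Four arguments stand against the point.

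- **Baseline MVIC is already in the primary analysis.** It is the first repeated measure. That is true, but analysing change fixes its coefficient at 1. Change still correlates with baseline at −0.50 to −0.22 over the range of ρ considered. The gains above come on top of the repeated measures analysis.
- **Blocking is not described.** A reader might infer that standard errors are certainly too large and that true type I error is below 5%. The documents do not support this: it needs balance within strata, and step 5 shows no miscalibration without it. Drop-out shrinks it further, as would an uneven cutoff (a 25/75 split with drop-out gave 3.6% and 4.2% at r = 0.5). This objection stands, so the calibration claim can only be conditional. The power loss does not depend on it.
- **Secondary outcomes.** A reader might infer that power is lost on every outcome related to leg strength. That does not follow. What matters is whether change, not level, tracks baseline MVIC, and the documents give no such correlation. At r = 0 there is nothing to gain.
- **Any error is conservative.** This also stands. The omission creates neither bias nor false positives.

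**Conclusion.** The point holds as a modest loss of efficiency. The trial stratifies on a variable that its between-arm analysis does not use as a factor or covariate. The cost is about 1 to 5 power points on MVIC for pre-post correlations of 0.9 to 0.5, and about 0 to 2 points on secondary outcomes if r is 0.3 or less. The conservative standard error is an additional effect only if allocation is balanced within strata.

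These sizes rest on assumed correlations, a median cutoff, equal SDs, random drop-out and, where stated, blocks of 4. None of these is given in the documents. Nor do they support extending the point to a stratified test for readmission: no between-arm test is named for that outcome, and no calculation here shows a gain.

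**What to change.** In Data analysis, add one sentence. The between-arm models for MVIC, SPPB, 6-minute walk, grip strength and CAT include the MVIC stratum as randomised, with its stratum-by-time term, and the treatment effect is the group-by-time term from that model. For the primary outcome, continuous baseline MVIC may be used instead, as an ANCOVA of post-training MVIC on group and baseline. It gains more (89.5% against 86.3% at ρ = 0.5). In Randomization, state whether the list is made separately per stratum and in blocks, so that readers can tell whether the calibration issue arises.

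The cost is one error degree of freedom per model, and at most about 1 power point if the correlation is zero. No new data are needed, because baseline MVIC and the stratum are known before allocation. Fixing the adjustment in advance also removes the option of choosing it after results are seen.

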Though there no adverse risk responses were reported in published

randomized controlled trials in clinical populations in the literature, there are some expected transient perceptual type responses, e.g. dizziness, limb numbness, perceived exertion, delayed onset muscle soreness. There are no significant risks of complications if BFR-RE is prescribed by certified trainers who have knowledge of appropriate protocols and contraindications to the use of occlusive stimuli. (Brandner, 2018)

The effect on muscle strength in COPDAE inpatients, which is not well studied in the literature, will be the primary outcome of this study. The effect on mobility functions, systemic muscle strength reflected by hand grip strength, health related quality of life and unplanned readmission rate within 1 month of discharge for COPDAE will be evaluated as secondary outcomes. Since BFR-RE is newly introduced to Haven of Hope Hospital and not widely used in Hospital Authority, acceptability and feasibility of this training will be explored as secondary outcomes.

Subjects

Patients with COPD acute exacerbation (COPDAE) will be recruited to find out the effect of blood flow restriction resistance exercise (BFR-RE). There will be a control group without BFR-RE for comparison. Principal investigator will screen the medical fitness of the subjects before recruiting to the study.

Inclusion criteria

1. COPD acute exacerbation (COPDAE) as the primary diagnosis for hospitalization or transfer to pulmonary wards of the Haven of Hope Hospital
2. Able to walk under supervision
3. Understand instruction in Cantonese and can give informed consent.

Exclusive criteria (Hick, 2013)

Subjects will be excluded if they have any of the following conditions:

1. Concomitant acute cardiac event	7. History of lymphectomies
2. Severe hypertension (BP > 180/100)	8. Extremities with dialysis access
	9. Vascular grafting

3. History of venous thromboembolism
4. History of peripheral vascular disease
5. Absence of posterior tibial or dorsalis pedal pulse
6. History of revascularization of the extremity
10. Current extremity infection
11. Active malignancy*
12. Open fracture / soft tissue injuries
13. Amputation to the lower extremity
14. Expected hospitalization less than 2 weeks on admission
15. Medications known to increase clotting risks
16. Isolation / Contact precaution requirement (e.g. MRSA status, CD toxin +ve status, etc.)

*Active malignancy (Kearon,2016) is defined as follow:

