The individual participant can withdraw from the study at any time. Participants

may also be excluded from the study at any time based on the investigator's evaluation.

Data registration

All data relevant for the study are recorded in a specific form.

Data of each enrolled participant are listed in a personal form.

Recruitment

Consecutive patients will be recruited in the three pulmonary wards in Haven of Hope Hospital between 10.6.2020 – 28.2.2021. The study will be expected to finish within 9 months or earlier if the expected recruitment achieved.

Expected Benefits

BFR-RE may improve the muscle strength of the knee extension and muscle size of quadriceps in the patients undergoing early rehabilitation for COPDAE. This may allow patients to actively participate the resistance training to improve the mobility function, subsequently health-related quality of life.

Adverse events

In this context, adverse events are defined as any unintended, unfavorable finding, symptom or disease that can be connected to the strength training, whether it is deemed to have a correlation with this or not. Adverse events are recorded by spontaneous registration as well as by open questioning.

Concerns on patient's safety

Delayed onset of muscle soreness (DOMS)

DOMS is normal after exercise, including after LL-BFR training. It was reported in 40% of participants in a survey before but this will subside within 24-72 hours (Patterson, 2018).

Numbness

Incidence of transient numbness is between <2% (Nakajima, 2006) to 18.5% (Patterson, 2018). This is related to the tourniquet pressure causing peripheral nerve compression.

Central vascular response

Continuous BFR-RE (keep restriction during rest period between sets) will

increase the heart rate (HR), systolic blood pressure (SBP), diastolic blood pressure (DBP), or double product (HR x SBP) compared with same exercise in free flow conditions.

Cardiac output is not affected by BFR during exercise since HR increases and stroke volume decreases proportionally compared to non-BFR groups. Changes in central hemodynamic response are blunted after BFR-RE when compared to HL-RE. However, there was reported to be 14.6% of fainting / dizziness related to BFR-RE (Patterson, 2018). The study is not blinded to the physical therapists; thus, the identification of any safety issues will be easy.

Venous thromboembolism (VTE)

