The incidence rate of VTE in general population in Asia was 0.2-0.26% (Klatsky, 2000). However, there are minimal adverse events related to this possible complication reported in BFR-RE literature. Most studies use blood markers to assess the risks of VTE BFR-RE. There is no rise in D-dimers, prothrombin fragment, thrombin-antithrombin III complex, C-reactive protein immediately after BFR-RE training or weeks after training (Madarame, 2013). The reported incidence rate of venous thrombus in a large epidemiologic questionnaire (Nakajima, 2006) in Japan was 0.055% and pulmonary embolism was 0.008%.

Moreover, BFR-RE demonstrated a stimulation of fibrinolytic system by increased tissue plasminogen activator (t-PA), a thrombus-degrading protein in the epithelial cells in healthy participants (Nakajima, 2007).

Other vascular concerns (Patterson, 2018)

There are reported superficial thrombophlebitis (0.8%) and subcutaneous hemorrhage (0.8%). Bruising was reported to be 13.1% (Nakajima, 2006).

Rhabdomyolysis

It is a clinical syndrome due to skeletal muscle damage and the release of potentially toxic substances into the circulation. The reported risk was between 0.07-0.2% (Thompson, 2018). The survey (Nakajima, 2006) in Japan revealed the low incidence of 0.008%. However, this risk was not extraordinarily higher than traditional HL-RE training.

Education

Observations and measurements are carried out by physiotherapists,

occupational therapists, doctors associated with the project.

Serious adverse events

In this context, serious adverse events are defined as events or reactions that cause:

- Death
- Life-threatening situations
- Urgent transferal to acute hospital or prolongation of existing hospitalization
- Permanent or severe disability/incapacity

Serious adverse events must be evaluated by the investigator for possible correlations with treatment in the intervention group, to consider whether there is a reasonable possibility that the adverse event has been caused by that.

The following factors are included in the evaluation:

- Consistency of time.
- Conformity with known effects of the treatment.
- Alternative reasons.

If a serious adverse event is considered to have a causal correlation with the treatment, the investigator must consider the study to be terminated ahead of time.

Ethics

The study will be conducted in accordance with the principles of the Helsinki Declaration.

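### The Interruption clause lets an investigator exclude a randomised participant from the study, not only from training, at any time and on no stated criterion, and nothing keeps that participant in follow-up or analysis

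*Combined protocol and SAP*

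**What the plan says.** The Interruption section gives participants the right to withdraw and then adds that they "may also be excluded from the study at any time based on the" investigator's judgement. No criterion, independent review or later assessment is attached.

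Other sections that bear on this:

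- **Randomization:** "The envelopes are opened after inclusion for the individual participant only". The power to exclude at any time therefore covers the period after allocation is known.
- **Blinding:** "Participants, doctors, nurses and involved Physiotherapists are for obvious reasons not blinded". Only the assessments at recruitment and on discharge are masked; they "will be carried out by blinded Physiotherapists without knowledge of treatment group".
- **Serious adverse events:** "Serious adverse events must be evaluated by the investigator for possible correlations with treatment in the intervention group".
- **Data collection timepoint:** the only measurement after baseline is placed "After completeness of training (i.e. at least 10 sessions of training").
- **Data analysis:** a multivariate repeated measures ANOVA, with no analysis population and no rule for missing values.
- **Secondary outcomes:** the drop-out rate and its reasons are described under feasibility, without a split by arm.
- **A standardized resistance training:** a separate remark already covers stopping a patient's training for dizziness or severe discomfort.

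**The concern.** Training can be stopped under its own rule, so the Interruption clause adds something different: the power to take a person out of the study. Whoever uses it may know the arm and will have seen how the patient is coping. If patients who tolerate or respond to the cuff poorly are excluded more readily than comparable controls, the patients left in the BFR-RE arm look better than those randomised to it.

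The protocol's own safety section gives reason to expect a difference between arms. It cites numbness in up to 18.5% and fainting or dizziness in 14.6% with BFR training, and only one arm wears the cuff. Exclusions made in good faith could therefore be lopsided. Blinding of the assessor does not help, because it protects the measurement and not the decision about who is measured. At about 24 per arm, each patient removed is roughly 4% of the arm (1/24).

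**Working it through.** **Step 1. Does the text permit it?** Set side by side, the sections give: exclusion from the study; at any time, which includes after the envelope is opened; on an investigator's judgement; with treating doctors and physiotherapists unmasked. The Blinding section does not use the word investigator. That the investigator knows the arm is inferred from doctors being listed as unblinded and from the investigator having to relate serious events to the intervention.

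**Step 2. Would an excluded patient leave the comparison?** The documents do not say so. But a repeated measures ANOVA with two timepoints needs both values, the second value is planned only after at least 10 sessions, and no analysis set or missing-data rule exists. A patient excluded before session 10 has no planned second value. One excluded later may have it, but nothing says that it will be used.

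**Step 3. Numbers per arm, from the plan.** Taking the printed f² = 0.22 with two equal groups, d = 2√0.22 = 0.938. Then n = 2(1.960 + 0.842)²/0.938² = 2 × 7.85/0.88 = 17.8, so 18 per group as stated (19 with the noncentral F). The stated total of 48 matches 18 × 1.3 = 23.4, rounded up to 24 per arm.

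**Step 4. Size of bias.** Assumptions: 24 per arm, no true effect, normally distributed gains in SD units, two-sided t-test at 0.05, and k patients removed from the BFR-RE arm only. Those removed rank lowest on a judgement that has correlation r with the true gain. Then

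bias = r × (sum of the k lowest expected normal order statistics of 24, sign reversed) / (24 − k).

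The three lowest are −1.948, −1.503 and −1.239.

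- k = 2: 3.451/22 = 0.157 at r = 1; 0.078 at r = 0.5; 0.047 at r = 0.3.
- k = 3: 4.690/21 = 0.223 at r = 1; 0.112 at r = 0.5; 0.067 at r = 0.3.

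Type I error comes from simulation with 40,000 trials per case (standard error near 5%: √(0.05 × 0.95/40,000) = 0.1 percentage point):

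| Pattern, one arm only | k = 2: bias; type I error | k = 3: bias; type I error |
|---|---|---|
| Unrelated to gain | 0; 5% | 0; 5% |
| r = 0.3 | 0.05 SD; 5.4% | 0.07 SD; 5.6% |
| Random from the lower half | 0.07 SD; 5.3% | 0.11 SD; 5.9% |
| r = 0.5 | 0.08 SD; 6.0% | 0.11 SD; 6.8% |
| Worst responders exactly (r = 1) | 0.16 SD; 9.3–9.5% | 0.22 SD; 13–14% |

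If both arms lose the same number by the same rule, the two biases cancel.

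**Step 5. Scale.** Against the design effect of 0.938 SD, the moderate cases amount to 0.05/0.938 = 5% up to 0.11/0.938 = 12% of it.

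**The case against.** Four objections have weight.

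1. **The clause does not mention the analysis.** A reader might infer that the plan deletes excluded patients from the ANOVA. It does not say so, and Data registration keeps a form for every enrolled participant. This stands: removal is a consequence of what is missing from the plan, not a stated rule.

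2. **Late exclusions need not reflect treatment.** Because "Principal investigator will screen the medical fitness of the subjects before recruiting to the study", a reader might infer that every later exclusion must rest on events after randomisation. That does not follow. Infection or isolation status, or a history of thromboembolism or vascular disease, could be present at entry and come to light later. This stands.

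3. **The larger figures are a worst case.** A reader might infer a type I error of 9% to 14%. That needs exact ranking on strength gain, in one arm only. MVIC is scheduled only at baseline and after training, and masked physiotherapists measure it, so the ranking cannot be known before the final test. The Ethics section discloses study data to the investigator during the trial, so exclusion after the final result is not ruled out, but no text describes it. The moderate rows are the more credible ones.

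4. **It overlaps with the 10-session timepoint.** For a patient excluded early, the outcome is lost through that rule. This stands in part. The clause still reaches patients who have completed 10 or more sessions, and it would remain if everyone were assessed at discharge.

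The drop-out description under feasibility is a partial safeguard. It reports losses but keeps nobody in the comparison.

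**Conclusion.** The point holds as a gap in what the plan allows. An investigator may exclude a randomised participant from the study, probably knowing the arm, with no criterion and with no provision for follow-up or analysis. The documents do not show that anyone was or will be excluded selectively, or that excluded patients are to be left out.

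Under moderate one-sided selection of 2 or 3 patients, the expected distortion is small: about 0.05 to 0.11 SD, with type I error of about 5.3% to 7%. It becomes serious (0.16 to 0.22 SD, 9% to 14%) only under exact selection of the worst responders in one arm. Bias is nil if exclusion is unrelated to response or symmetric. These figures assume 24 per arm, normal gains and no true effect; the selection pattern is assumed and not taken from the plan. The clause should be changed because the remedy is cheap and, without it, a reader of the results could not tell which case applied.

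**What to change.** Separate two things that the clause merges. Stopping training stays wholly with the investigators, and no change to that is proposed. For study status, state the following:

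- A participant whose training is stopped remains in the study.
- He or she has the blinded discharge assessment that the Blinding section already plans, whatever the number of sessions completed. The exceptions are withdrawal of consent or an assessment that cannot be done (for example death, transfer or unsuitability for testing).
- The Data collection timepoint section is amended to match. At present it gives no second measurement to someone who stops before 10 sessions, so rewording Interruption alone would not work.
- Every participant is analysed in the randomised group using all data collected, and the plan says how a missing second value is handled.
- Training stops and study exits are reported separately, by arm and with reasons, including ineligibility found late. This extends the drop-out description already planned.

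The cost is a few sentences in three sections (Interruption, Data collection timepoint and Data analysis) and a few extra assessments by assessors already in place. The effect will be somewhat diluted by participants who trained less; that is the price of keeping the groups as randomised.
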